6.5 Safety endpoints

In addition to the standardized collection of AEs, safety data specific to insomnia and its treatment will be assessed as follows:

- Withdrawal effects (physical dependence) upon treatment discontinuation will be assessed based on the changes from last assessment on DB treatment (Visit 8, 2nd morning) to run-out period in the BWSQ total score (Visit 9 and Visit 10), the occurrence of relevant AEs and marked ECG abnormalities.
- Rebound insomnia will be assessed based on objective sleep parameters (WASO, LPS and TST) at Visit 9 as compared to Visit 3. It will also be assessed using subjective sleep parameters (sWASO, sLSO and sTST) from run-out period as compared to baseline.
- Next-day residual effect will be assessed based on changes from baseline (Visit 3) to Month 1 and Month 3 in:
 - Coding sub-test[©]
 - SDS[©]
 - Scores on the VAS (mm)
- SAEs up to 30 days after DB study treatment discontinuation or until enrollment into the extension study.
- TEAEs up to 30 days after DB study treatment discontinuation or until enrollment into the extension study.

- AEs leading to premature discontinuation of the DB study treatment.
- AEs of special interest after adjudication by ISB:
 - narcolepsy-like symptoms (i.e., EDS, cataplexy and complex sleep behavior events including hallucinations/sleep paralysis)
 - suicide/self-injury
- Change from baseline (Visit 3) to Month 1 (Visit 6) and Month 3 (Visit 8) in vital signs (mean of the 2 PSG nights in systolic and diastolic blood pressure [BP] and pulse rate).
- Change from baseline (Visit 1) to Month 3 (Visit 8) in body weight.
- Marked ECG abnormalities on DB study treatment.
- Change from baseline (Visit 3) to Month 3 (Visit 8) and the end of the run-out period (Visit 10) in ECG parameters.
- Marked laboratory abnormalities on DB study treatment.
- Change from baseline (Visit 3) to Month 1 (Visit 6) and Month 3 (Visit 8) in laboratory parameters.
- Occurrence of suicidal ideation and/or behavior on DB study treatment based on C-SSRS[®].

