7.2.3.12 ECG assessment

A standard 12-lead ECG is to be performed at Visit 1, in the second morning of Visit 3, Visit 8 and at Visit 10.

12-lead ECG will be recorded at rest with the subject in the supine position. Data records will be sent to the evaluation center for central reading.

Details will be provided in the 12-lead ECG laboratory manual.

The following parameters will be evaluated: PQ or PR (ms), QRS (ms), QT (ms), heart rate (HR; bpm), and rhythm. QTc (ms) will be calculated according to:

- Bazett's formula: $QTcB = QT / (RR)^{1/2}$
and
- Fridericia's formula: $QTcF = QT / (RR)^{1/3}$, where $RR = 60 / HR$

If the central review of the ECG detects a prolonged QTcB and/or QTcF interval greater than 450 ms for a subject at screening (Visit 1 or Visit 3), the ECG must be repeated (at least 30 min after first ECG). If the central review confirms that the repeated ECG shows

a QTcB and/or QTcF interval greater than 450 ms, the subject cannot be enrolled into the study.

Clinically significant findings detected after signing of ICF which meet the definition of an AE must be recorded in the eCRF.

ECG data collected by the CRO will be electronically transferred to Idorsia.

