7.4 Electrocardiography

Unless noted otherwise, ECG summaries and listings will include scheduled, re-test and unscheduled assessments.

Descriptive summary statistics for each scheduled visit (re-test excluded) will be provided for observed values and change from baseline in ECG parameters (QT corrected according to Fridericia's formula, QT corrected according to Bazett's formula, heart rate, PR, QRS).

Marked ECG abnormalities are defined in [Table 5](#). The following summaries will be provided for each ECG parameter:

- Number (%) of subjects with a marked ECG abnormality during the DB study period.
- Number (%) of subjects with a marked ECG abnormality during the treatment withdrawal period (based on the TWS).

Percentages will be based on the number of subjects at risk, i.e., those having at least one post-baseline value in the study period under consideration per ECG parameter for criteria based on post-baseline values only, or those having a baseline value and at least one post-baseline value in the study period under consideration per ECG parameter for criteria based on change from baseline. For non-mutually exclusive criteria (i.e., HR, PR, and QRS), a subject will be counted only once in case of multiple occurrences but may be reported in more than one marked ECG abnormality criterion of a given parameter. For mutually exclusive criteria (i.e., QTc), only the subject's worst post-baseline value (or worst change from baseline value) will be counted.

ECG findings during the DB study period and during the treatment withdrawal period (based on the TWS) will be summarized separately and listed. ECG abnormality categories and findings will be sorted by descending frequency, first in the highest ACT-541468 dose level, then in the next highest ACT-541468 dose level, and finally in the placebo treatment group. After this sorting, ECG abnormality categories will be presented in alphabetical order with ECG finding sorted within ECG abnormality category in alphabetical order. All ECG values for subjects with at least one marked ECG abnormality during the DB study period or during the treatment withdrawal period will be listed.

Table 5 **Marked abnormalities in ECG parameters**

ECG parameter	Criteria for marked ECG abnormalities
QTcF, QTcB (ms)	> 450 and \leq 480 > 480 and \leq 500 > 500 > 30 and \leq 60 increase from baseline > 60 increase from baseline
HR (bpm)	< 45 < 50 > 10 and \leq 20 decrease from baseline > 20 decrease from baseline
PR (ms)	> 200

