7.5 Vital signs and body weight

Each summary will include only scheduled assessments (re-test excluded) and listings will include both scheduled and unscheduled assessments.

The change from baseline (mean of the two PSG nights at Visit 3, run-in period) to Month 1 (mean of the two PSG nights at Visit 6), Month 2 (Visit 7), Month 3 (mean of the two PSG nights at Visit 8) and Run-out period (Visit 9 and Visit 10) in vital signs (systolic and diastolic blood pressure, and pulse rate) will be summarized. The observed values at baseline and each scheduled post-baseline visit will also be summarized.

The change from baseline (Visit 1 or last value before DB study treatment) to Visit 8 (or last value on study) in body weight will be summarized.

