7.6 Withdrawal symptoms

The TWS will be used to assess the potential for withdrawal symptoms.

The BWSQ assesses the main symptoms which might be experienced by subjects during withdrawal from benzodiazepines.

The questionnaire consists of 20 items with each item rated by the subject as either 0 (No), 1 (Yes-moderate) to 2 (Yes-severe). The BWSQ Total score (possible range: 0 to 40) for the change from the last available assessment on DB study treatment to the beginning and the end of the treatment withdrawal period (in the morning at Visit 9 and at Visit 10, respectively) will be summarized. Observed values will also be summarized.

The number (%) of subjects with a BWSQ Total score above 20 will be tabulated by visit.

The number (%) of subjects with one or more BWSQ symptom scored as ‘severe’ will be tabulated by visit.

In addition, withdrawal symptoms after DB study treatment discontinuation will be assessed through the incidence of AEs, and marked ECG abnormalities, occurring during the treatment withdrawal period [see Section 12.2]. As described in their respective section, the incidence of AEs [Section 7.2] and marked ECG abnormalities [Section 7.4] occurring during the treatment withdrawal period (between Visit 9 and Visit 10) will be summarized.

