12.4 Baseline

Baseline is the last non-missing assessment performed or value measured before or on the day of first dose of DB study treatment, unless otherwise defined in the specific analysis section.

An assessment done on the day of the DB study treatment start date is considered a baseline assessment and is not considered a post-baseline assessment in the DB study period.

Subjects with no data on a particular parameter before the first treatment administration will have a missing baseline (and change from baseline) for this parameter.

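### SAP Table 5 has no criterion for a high or rising heart rate in the withdrawal period, and run-out ECG, pulse and blood-pressure changes are taken only from Visit 3

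*SAP*

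**What the plan says.** Protocol 6.5 assesses withdrawal effects by the change in BWSQ total score together with "the occurrence of relevant AEs and marked ECG abnormalities". SAP 7.6 repeats the three components, and SAP 7.4 tabulates marked ECG abnormalities in the treatment withdrawal period on the treatment withdrawal set (TWS).

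Table 5 in SAP 7.4 gives the criteria for both the double-blind and the withdrawal period. For heart rate there are four: below 45 bpm, below 50 bpm, and two bands of fall, where the table text ends "20 decrease from baseline > 20 decrease from baseline".

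The reference values differ within the same assessment:

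- **BWSQ** (SAP 7.6) is summarized "for the change from the last available assessment on DB study treatment to the beginning" and the end of the withdrawal period.
- **ECG** (Protocol 6.5): "Change from baseline (Visit 3) to Month 3 (Visit 8) and the end of the run-out period (Visit 10) in ECG parameters". SAP 7.4 names no reference of its own, so the general rule in SAP 12.4 applies: "Baseline is the last non-missing assessment performed or value measured before or on the day of first dose of DB study treatment". Protocol 7.2.3.12 states: "A standard 12-lead ECG is to be performed at Visit 1, in the second morning of Visit 3, Visit 8 and at Visit 10". The baseline is therefore normally Visit 3, and Visit 10 is the only scheduled run-out ECG.
- **Vital signs** (SAP 7.5): "The change from baseline (mean of the two PSG nights at Visit 3, run-in period) to Month 1" and later visits, "and Run-out period (Visit 9 and Visit 10) in vital signs".

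**The concern.** A withdrawal screen asks what happens to a subject when drug is replaced by placebo. The documents do not say in which direction heart rate would move, so the screen should be able to register either. Table 5 looks one way only. A one-sided rule may have been reasoned for the on-drug period, but it is carried over unchanged to the period after discontinuation, and the SAP gives no reason. Two-sided limits are familiar in this SAP: Table 4 uses them for potassium, glucose and TSH, among others.

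The choice of reference is a second, separate matter. Change from Visit 3 shows where the subject stands relative to the pre-treatment state. It does not show the within-subject change on stopping, which is what the BWSQ analysis measures. If heart rate on drug differs from Visit 3, the two answers differ and may have opposite signs.

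At stake is how a reassuring withdrawal table is read. A low count of marked heart-rate abnormalities in run-out would say nothing about rises.

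**Working it through.** The plan states no figure to reproduce here. The check applies its criteria to example values. All heart rates and QTcF values below are assumptions chosen for illustration.

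**1. The heart-rate criteria.** Let d = HR(Visit 3) − HR(Visit 10). Table 5 flags if HR(Visit 10) < 45, if HR(Visit 10) < 50, if 10 < d ≤ 20, or if d > 20. When Visit 10 exceeds Visit 3, d is negative and both change criteria fail by construction. If Visit 3 is also at least 50 bpm, both low limits fail too. A grid of Visit 3 values from 50 to 110 bpm, with every higher whole-number Visit 10 value up to 160, has 61 × 80 = 4,880 combinations. None is flagged. (Below 50 bpm a subject could be flagged after a rise, but for being low.)

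**2. Worked subjects (bpm).**

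| Visit 3 | Visit 8 | Visit 10 | From Visit 3 | From Visit 8 | Table 5 HR flag |
|---|---|---|---|---|---|
| 70 | 60 | 90 | +20 | +30 | none |
| 70 | 70 | 110 | +40 | +40 | none |
| 60 | 60 | 130 | +70 | +70 | none |
| 70 | 50 | 70 | 0 | +20 | none |
| 80 | 55 | 65 | −15 | +10 | fall > 10 and ≤ 20 |

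The first three rows show the missing criterion. The last two show the effect of the reference: a 20 bpm rise off drug appears as no change, and a 10 bpm rise is counted as a fall.

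**3. The two issues are independent.** With Visit 8 as reference and Table 5 unchanged, a rise from Visit 8 still gives a negative d, so no change criterion fires. With increase rows added but Visit 3 kept, 70/50/70 still shows zero and 80/55/65 still shows −15. Each issue needs its own repair.

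**4. Indirect route through QTcB.** From the formulas in Protocol 7.2.3.12, QTcB = QTcF × (HR/60)^(1/6). Hold QTcF constant at an assumed value between 390 and 420 ms:

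- HR 60 to 100: QTcB rises 34.7 to 37.3 ms, which meets the criterion of more than 30 ms.
- HR 60 to 95: factor (95/60)^(1/6) − 1 = 0.0796, so 390 × 0.0796 = 31.0 ms to 420 × 0.0796 = 33.4 ms; flagged.
- HR 60 to 90: 27.3 to 29.4 ms; not flagged.
- HR 70 to 95 at QTcF 400 ms: 410.4 to 431.8 ms, a rise of 21.4 ms; not flagged. If Visit 8 was 60 bpm, that subject rose by 35 bpm off drug.

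A large rise can therefore enter the table, but under a QTc label and depending on the Visit 3 rate and QTcF.

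**5. Other routes in the plan.** Adverse events that start or worsen in the withdrawal period are tabulated on the TWS (SAP 7.2), and clinically significant ECG findings meeting the AE definition must be recorded (Protocol 7.2.3.12). Reported ECG findings in the withdrawal period are summarized apart from Table 5 (SAP 7.4). Observed heart rate and pulse are summarized at each scheduled visit (SAP 7.4, 7.5) with n, mean, SD, median, quartiles, minimum and maximum (SAP 10.2). Safety data are listed (SAP 7.1), although the ECG-value listing described in SAP 7.4 covers only subjects with a marked abnormality.

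**The case against.** A reader might infer that a heart-rate rise after stopping drug can never count as a withdrawal effect. The documents do not support that. Adverse events are themselves a named withdrawal component, and the routes in step 5 and sometimes QTcB remain open. Nor are the pulse summaries limited to means: the maximum and SD of the change at Visits 9 and 10 could reveal a few large rises.

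The Visit 3 reference also has a case. It follows the protocol's ECG endpoint, it is the pre-treatment reference used for rebound insomnia, and it shows overshoot beyond the untreated state. It hides a rise only if heart rate was lower on drug, which no section claims. Visit 8 can be set beside Visits 9 and 10 by arm from the observed values. Protocol 1.4.1 rates withdrawal symptoms as unlikely, and the SAP already added run-out vital signs (SAP 13.4).

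These points stand and limit the concern. They do not remove it. Adverse events and reported findings depend on someone judging the rise notable. By-visit summaries give neither the number of subjects who rose nor any within-subject change from Visit 8. SAP 7.6 does not name vital signs as a withdrawal measure, and SAP 7.5 gives them no categorical criteria.

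**Conclusion.** The point holds as a limited gap in a descriptive safety analysis. As written, no Table 5 heart-rate criterion detects a high or rising rate in the withdrawal period, and no change from the last on-drug value is planned for ECG, pulse or blood pressure. A rise from a lowered on-drug value that stays below Visit 3 can be reported as a decrease.

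The absence of an upward criterion follows from the table alone. The size of any distortion from the Visit 3 reference depends on how far on-drug values depart from Visit 3, which the documents do not give; the examples show what is possible, not what is expected. The Visit 3 reference does not cause the missing flag. No primary or secondary efficacy result is touched.

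**What to change.** For the treatment withdrawal period, on the TWS:

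1. Add heart-rate increase rows to Table 5 that mirror the decrease rows (more than 10 and up to 20 bpm; more than 20 bpm), plus a high heart-rate reporting limit chosen by the sponsor. The documents offer no value for that limit, and none is suggested here. State the reference for the new rows; only a Visit 8 reference would pick up a subject such as 70/50/70.
2. Summarize ECG change from Visit 8 to Visit 10, and pulse and blood-pressure change from Visit 8 to Visits 9 and 10, beside the planned change from Visit 3.

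The cost is SAP wording and a few extra descriptive rows on measurements already scheduled, with no new visits and no effect on the testing strategy. The gain on the ECG side is bounded, because Visit 10 is the only scheduled run-out ECG. The Visit 9 pulse and blood pressure are the vital-sign measurements closest to stopping, so the second item matters most there.

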7.5 Vital signs and body weight

Each summary will include only scheduled assessments (re-test excluded) and listings will include both scheduled and unscheduled assessments.

The change from baseline (mean of the two PSG nights at Visit 3, run-in period) to Month 1 (mean of the two PSG nights at Visit 6), Month 2 (Visit 7), Month 3 (mean of the two PSG nights at Visit 8) and Run-out period (Visit 9 and Visit 10) in vital signs (systolic and diastolic blood pressure, and pulse rate) will be summarized. The observed values at baseline and each scheduled post-baseline visit will also be summarized.

The change from baseline (Visit 1 or last value before DB study treatment) to Visit 8 (or last value on study) in body weight will be summarized.

7.6 Withdrawal symptoms

The TWS will be used to assess the potential for withdrawal symptoms.

The BWSQ assesses the main symptoms which might be experienced by subjects during withdrawal from benzodiazepines.

The questionnaire consists of 20 items with each item rated by the subject as either 0 (No), 1 (Yes-moderate) to 2 (Yes-severe). The BWSQ Total score (possible range: 0 to 40) for the change from the last available assessment on DB study treatment to the beginning and the end of the treatment withdrawal period (in the morning at Visit 9 and at Visit 10, respectively) will be summarized. Observed values will also be summarized.

The number (%) of subjects with a BWSQ Total score above 20 will be tabulated by visit.

The number (%) of subjects with one or more BWSQ symptom scored as ‘severe’ will be tabulated by visit.

In addition, withdrawal symptoms after DB study treatment discontinuation will be assessed through the incidence of AEs, and marked ECG abnormalities, occurring during the treatment withdrawal period [see Section 12.2]. As described in their respective section, the incidence of AEs [Section 7.2] and marked ECG abnormalities [Section 7.4] occurring during the treatment withdrawal period (between Visit 9 and Visit 10) will be summarized.

7.7 Rebound insomnia

The TWS will be used to assess the potential for rebound insomnia. The change from baseline (Visit 3) to the treatment withdrawal period (Visit 9, run-out) in objective sleep parameters (WASO and LPS) will be summarized. The change from baseline (mean value based on the screening sleep diary entries performed at home in the 7 days immediately preceding the first PSG at Visit 3) to the treatment withdrawal period (after PSG night at Visit 9 [see Section 12.8]) in the subjective sleep parameter sTST will be summarized. Empirical cumulative distribution function plots of these objective and subjective sleep parameters for each treatment group will be provided, together with a summary showing the cumulative number and percentage of subjects meeting a certain threshold for the observed range of values.

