4.3 Inclusion criteria

For inclusion in the study, all of the following inclusion criteria must be fulfilled. It is not permitted to waive any of the criteria for any subject.

Criteria assessed at Visit 1

1. Signed informed consent prior to any study-mandated procedure.
2. Male or female aged ≥ 18 years.

3. Insomnia disorder according to DSM-5 criteria as follows:
 - 3.1 The predominant complaint is dissatisfaction with sleep quantity or quality, associated with one (or more) of the following symptoms:
 - Difficulty initiating sleep.
 - Difficulty maintaining sleep, characterized by frequent awakenings or problems returning to sleep after awakenings.
 - Early-morning awakening with inability to return to sleep.
 - 3.2 The sleep disturbance causes clinically significant distress or impairment in social, occupational, educational, academic, behavioral, or other important areas of functioning.
 - 3.3 The sleep difficulty occurs despite adequate opportunity for sleep.
 - 3.4 The insomnia is not better explained by and does not occur exclusively during the course of another sleep-wake disorder (e.g., narcolepsy, a breathing-related sleep disorder, a circadian rhythm sleep-wake disorder, a parasomnia).
 - 3.5 The insomnia is not attributable to the physiological effects of a substance (e.g., a drug of abuse, a medication).
 - 3.6 Coexisting mental disorders and medical conditions do not adequately explain the predominant complaint of insomnia.
 - 3.7 Self-reported history of all the following on at least 3 nights per week and for at least 3 months prior to Visit 1:
 - 3.7.1 ≥ 30 min to fall asleep, and
 - 3.7.2 Wake time during sleep ≥ 30 min, and
 - 3.7.3 $sTST \leq 6.5$ h
4. ISI[®] score ≥ 15 .
5. Ability to communicate well with the investigator, to understand the study requirements and judged by the investigator to be alert and oriented to person, place, time, and situation.

Criteria assessed at Visit 3

6. Meeting all the following sleep parameters on at least 3 nights out of 7 nights on the sleep diary completed at home between Visit 2 and Visit 3:
 - 6.1 ≥ 30 min to fall asleep, and
 - 6.2 Wake time during sleep ≥ 30 min, and
 - 6.3 $sTST$ of ≤ 6.5 h
7. Usual bedtime between 21:30 and 00:30, as reported on sleep diary completed between Visit 2 and Visit 3.
8. Regular time in bed between 6 and 9 h, as reported on sleep diary completed between Visit 2 and Visit 3.
9. Meeting all the following sleep parameters on the 2 PSG nights at Visit 3:

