6.1 Primary efficacy endpoints

The primary efficacy endpoints of this study are defined as:

- the change from baseline to Month 1 in WASO (sleep maintenance)
- the change from baseline to Month 3 in WASO
- the change from baseline to Month 1 in LPS (sleep onset)
- the change from baseline to Month 3 in LPS

Baseline is defined as the mean of the 2 PSG nights at Visit 3. Month 1 and Month 3 are defined as the mean of the 2 PSG nights at Visit 6 and Visit 8, respectively.

LPS (min) is the time from start of recording to the beginning of the first continuous 20 epochs (i.e., 10 min) scored as non-awake, i.e., epochs scored as either sleep stage 1 (S1), sleep stage 2 (S2), sleep stage 3 (slow wave sleep [SWS]) or REM, as determined by PSG.

WASO is the time (min) spent awake after onset of persistent sleep until lights on, as determined by PSG.

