The changes from baseline to the treatment withdrawal period (Visit 9, run-out) in objective sleep parameters (WASO, LPS and TST) will be summarized using descriptive statistics.

The changes from baseline (mean value based on the screening sleep diary entries performed at home in the 7 days immediately preceding the first PSG at Visit 3) to the treatment withdrawal period (after PSG night at Visit 9) in subjective sleep parameters (sWASO, sLSO, and sTST) will be summarized using descriptive statistics.

Next-day residual effect

Observed values and changes from baseline to Month 1 and Month 3 in Coding sub-test[®], SDS[®], and VAS scores (mm) assessing morning sleepiness, daytime alertness and daytime ability to function, will be summarized.

C-SSRS[®]

Number (%) of subjects with suicidal ideation, suicidal behavior, and/or self-injurious behavior without suicidal intent based on the C-SSRS[®] during DB treatment will be tabulated.

Shifts from baseline showing any changes in suicidal ideation and suicidal behavior during DB treatment will also be provided. Subjects will be summarized under the worst of the following three categories, shown here in the order from best to worst: 1) No suicidal ideation or behavior, 2) Suicidal ideation only, and 3) Suicidal ideation and behavior.

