1 INTRODUCTION

This statistical analysis plan (SAP) describes in detail the analyses and data presentation for the clinical study report (CSR) prepared for ID-078A301.

Obvious corrections to address minor formatting errors or spelling mistakes may be performed at the time of analysis without amending this and related documentation (e.g., mock shells).

Data will be analyzed by Idorsia and/or designated contract research organizations supervised by Idorsia using SAS[®] version 9.4 or higher and R version 3.4.3 or higher.

The analyses for the Independent Data Monitoring Committee (IDMC) closed session meetings will be performed by an Independent Statistical Analysis Center (ISAC) and are detailed in a separate SAP.

Protocol ID-078A301, Final Version 4, dated 30 July 2018 was used when writing this SAP.

A sub-study will be performed to collect data on subject preferences, which aims to enroll at least 360 subjects from the USA and Germany who are part of the approximately 900 subjects enrolled in the ID-078A301. The statistical analyses of the sub-study will be detailed in a separate document and reported separately.

Unless noted otherwise, summaries will be produced by treatment group [see Section 10.2].

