6.1.7 Sensitivity analyses

The incidence and pattern of missing values will be explored to assess the appropriateness of the statistical analysis and possible impact on results. The observed missing data patterns for WASO, LPS, sTST and IDSIQ Sleepiness domain score at Baseline, Month 1 and Month 3 will be presented for each treatment group. The missing data patterns will be sorted from completely missing to completely observed by the order of the first occurrence of missing data.

The mean change from baseline of the primary and secondary efficacy endpoints will be plotted over time (to Month 1 and to Month 3) for study completers and for premature study withdrawals by treatment group and by reason for study discontinuation together with a summary table. A cumulative incidence plot will be provided showing the timing (relative to randomization date) and reasons for premature DB study treatment discontinuation and premature study discontinuation, separately, by treatment group. Based on the exploration of the observed missing data patterns, further sensitivity analyses to those described below may be performed.

The linear mixed effects model (or mixed model for repeated measures [MMRM]) relies on the missing at random (MAR) assumption. That is, conditional on the statistical model and observed values of the outcome (e.g., change from baseline WASO), the probability of missing data does not depend on the unobserved values of that outcome. Consequently,

the subject's missing values are estimated based on similar subjects who remain in the study.

Performing the main analysis under MAR is not likely to bias results in favor of ACT-541468 to an important degree, especially if the proportion of withdrawals are similar across treatment groups (or not significantly greater in the ACT-541468 groups), and subjects who withdraw early for a given reason tend to have similar outcomes before withdrawal (e.g., less favorable than completers) across treatment groups. In addition, assuming missing data are MAR in the placebo group is considered conservative; subjects who withdraw are expected to have worse efficacy over time compared to those placebo subjects that remain, whose data will constitute the basis for the imputed values for the withdrawn subjects. Furthermore, a placebo effect is expected to increase (improve) over time, particularly in those subjects on placebo who remain in the study.

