10.2 General rules for data presentations

Data are listed and summarized as described below.

The tables will use the following header structure (label and order):

ACT-541468 25 mg N = xxx	ACT-541468 50 mg N = xxx	Placebo N = xxx
---	---	----------------------------------

Where N indicates the total number randomized or treated appropriate to the analysis set in the corresponding treatment group, unless otherwise specified.

All listings will be sorted by randomized treatment or actual treatment received (appropriate to the analysis set), country, subject number (ascending) and, when appropriate, by visit / date of assessment (ascending). Listings related to the SCR set will present a treatment group label “screening failure” to indicate subjects who were not

randomized and will be listed after the subjects who were randomized or received DB study treatment, as relevant.

Unless noted otherwise, the following descriptive statistics will be used to summarize data: number (%) of subjects for categorical variables or descriptive statistics (number of non-missing values, mean, SD, median, Q1, Q3, minimum, maximum) for continuous variables.

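### Rebound insomnia is summarised only as each arm's change from a baseline that also decides eligibility; a pre-specified difference from placebo with a confidence interval would be a cheap and useful addition

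*SAP*

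**What the plan says.** SAP section 7.7 defines the objective part of the rebound assessment: "The change from baseline (Visit 3) to the treatment withdrawal period (Visit 9, run-out) in objective sleep parameters (WASO and LPS) will be summarized". For sTST it compares the run-out diary with the seven run-in diary days before Visit 3. Protocol section 10.3.3 takes the same approach, "in objective sleep parameters (WASO, LPS and TST) will be summarized using descriptive statistics"; SAP section 13.1 openly drops TST, sWASO and sLSO from the rebound assessment. The analysis set is the Treatment Withdrawal Set.

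On the reference point, protocol section 6.1 states: "Baseline is defined as the mean of the 2 PSG nights at Visit 3". The same nights are an entry gate in protocol section 4.3: "Meeting all the following sleep parameters on the 2 PSG nights at Visit 3". The thresholds are mean LPS of at least 20 min, mean WASO of at least 30 min and mean TST below 420 min, with minimum values for each night on LPS and WASO. Criterion 6 in that section applies a similar gate to the run-in diary, which supplies the sTST baseline.

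On display, SAP section 1 says: "Unless noted otherwise, summaries will be produced by treatment group". Section 10.2 gives columns for 25 mg, 50 mg and placebo, and lists n, mean, SD, median, quartiles and range as the default statistics. Section 7.7 adds: "Empirical cumulative distribution function plots of these objective and subjective sleep parameters for each treatment group will be provided". Neither document gives a difference from placebo, a confidence interval or a numerical definition of rebound.

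**The concern.** Visit 3 is not a neutral reference for a subject who is off drug at about Day 85, for two reasons. Subjects enter because they slept badly on those nights, so some drift towards better values is expected. In addition, SAP section 6.1.7 says that "a placebo effect is expected to increase (improve) over time". Both push later values in every arm towards apparent improvement.

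An active arm whose run-out value equals its baseline would then show no change. It could still be sleeping worse than placebo subjects who went through the same selection and the same three months. At Visit 9 every arm takes placebo, so the concurrent placebo arm is the natural comparator.

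The safety objective explicitly covers treatment discontinuation, so rebound is likely to be the subject of a conclusion in the study report. SAP sections 6.1.4 and 6.2 provide placebo-adjusted means with 95% CIs for the primary, secondary and other efficacy endpoints. Section 7.7 provides nothing equivalent, and the choice of comparison that would support a statement about rebound is left until after unblinding.

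**Working it through.** **The plan's own figure.** Protocol section 10.5 states 98.9% power with 300 per arm, effect size 0.37 and two-sided alpha of 2.5%. Noncentrality = 0.37 / √(2/300) = 4.53; critical value = 2.24; power = Φ(4.53 − 2.24) = 0.989. This reproduces, and 0.989⁹ = 0.905 agrees with the stated 90% for nine independent tests. The documents give no corresponding figure for rebound.

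**How masking works.** Let R be the true worsening of an active arm relative to concurrent placebo in run-out, and P the placebo arm's own improvement from Visit 3 to Visit 9. The active arm's change from baseline is then R − P, while the placebo-adjusted difference is R whatever the value of P.

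For illustration take R = 15 min, which is the difference from placebo that section 10.5 treats as minimally relevant for WASO and LPS efficacy. It is not a rebound threshold. P is assumed, because the documents do not state it. With SD 40 (Table 2) and n = 300, the within-arm 95% CI is ± 1.96 × 40/√300 = ± 4.5 min.

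| Assumed P (min) | Active arm, change from baseline (min) | Difference from placebo (min) |
|---|---|---|
| 0 | +15 | +15 |
| 5 | +10 | +15 |
| 10 | +5 | +15 |
| 15 | 0 | +15 |
| 20 | −5 | +15 |

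The distribution plots would still separate the arms. At P = 20, a normal approximation puts Φ(−5/40) = 45% of active subjects above their baseline, against Φ(−20/40) = 31% of placebo subjects.

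**How much of P comes from selection.** Nights were simulated as log-normal, with assumed median LPS of 25 to 45 min, median WASO of 50 to 90 min, between-subject log SD of 0.5 and night-to-night log SD of 0.4 to 0.6. After applying the Visit 3 thresholds, the expected change to a later untreated night ranged from under 1 min of improvement up to 4.3 min for LPS and 4.2 min for WASO. Selection alone is therefore small. The remainder of P would be placebo response and time, for which the documents give a direction but no size.

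**Precision of the added contrast.** Half-width = 1.96 × SD × √(2/n).

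- WASO or LPS, n = 300, SD 40: 6.4 min.
- n = 270 (assumed size of the Treatment Withdrawal Set per arm), SD 40: 6.7 min.
- n = 270, SD 55 (assumed, because Visit 9 is a single night): 9.3 min.
- Least favourable case considered, n = 240 and SD 60 (both assumed): 10.7 min.
- sTST, SD 54 (Table 2), n = 300 down to 240: 8.6 to 9.7 min.

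**The case against.** The strongest reply is that the placebo course is already on show. A reader might infer that the plan conceals it, and the documents do not support that. Tables carry a placebo column, the distribution plots are drawn for every arm, and an unadjusted difference with its interval can be worked out from the reported n, mean and SD. This stands. The gap is a pre-specified estimate and a stated reading, not missing information.

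It also stands that neither document sets a pass/fail rule, so nothing tells the reader to ignore placebo. Other safety variables are likewise summarised descriptively, so the approach is consistent within the plan. Protocol section 3.2.1 says that the placebo run-in is meant to reduce the placebo effect and may reduce regression to the mean, although it cannot remove selection on the Visit 3 nights themselves.

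A further reply is that the protocol defines rebound against the pre-treatment level, and that a placebo contrast would mix rebound with simple loss of benefit. The first half is right, and is why the change from baseline should stay. The second half does not hold. All arms take placebo at Visit 9, so an active arm that merely loses its drug effect should fall back to the placebo arm's level and give a difference near zero.

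It may be tempting to call the contrast unbiased because treatment was randomised. It is not: under protocol section 5.1.9, subjects who stop treatment early skip the run-out, so the Treatment Withdrawal Set is selected after randomisation. It may also be tempting to argue that Visit 9, following directly on two laboratory nights, is biased in a particular direction. The conditions do differ from Visit 3, but the documents give no direction or size, and sTST excludes laboratory nights altogether.

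**Conclusion.** The point holds as a cheap improvement, not as an error that invalidates the rebound assessment. The planned measure follows the protocol's definition. However, its reference also decides eligibility, the SAP expects placebo subjects to improve from it, and no placebo-adjusted estimate or interval is pre-specified.

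The possible masking equals the placebo arm's own improvement from Visit 3 to run-out. Selection accounts for about 0 to 4 min of that for WASO and LPS, under the assumed distributions; no masking size was derived for sTST. A reader might infer from the table of assumed values that masking will reach 15 min. The documents do not support this: they say the placebo effect should grow but not by how much, and that table is conditional arithmetic.

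The contrast would be informative. Across the assumed range (240 to 300 per arm, SD 40 to 60) the half-width for WASO and LPS is 6.4 to 10.7 min, below 15 min throughout.

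**What to change.** In SAP section 7.7, keep the by-arm change from baseline and the distribution plots as the protocol-defined measure, and add:

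1. The difference between each dose and placebo in change from baseline, with a 95% CI, for WASO and LPS at Visit 9 and for sTST in run-out. Use ANCOVA with baseline and age group as covariates, in the Treatment Withdrawal Set, descriptively and with no alpha allocated.
2. A sentence stating that rebound is interpreted from the change from baseline and the placebo-adjusted difference together.
3. A footnote that early discontinuers do not enter run-out, so the contrast is not fully protected by randomisation.

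The cost is one more table and a few lines of SAP text. No additional subjects, visits or measurements are needed, and the testing strategy is untouched.
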